The toxicity profile of GS-5718 was assessed in safety pharmacology and repeat dose toxicity studies in rats and monkeys, and in a battery of genotoxicity studies. GS-5718 was nongenotoxic in the studies evaluated and had no effects on the central nervous and respiratory systems of rats. GS-5718-related mild QT prolongation was observed at the high dose level in the cardiovascular safety pharmacology study in monkeys; however, given the small magnitude of change and exposure margin at this dose level (6-fold over the projected steady state free C_{max} at the 115 mg dose in humans), the risk for QT effects at clinically relevant exposures is considered low. There were no GS-5718-related adverse effects in 1-month rat and monkey repeat dose toxicity studies up to the highest dose levels tested. Steady-state AUC exposure margins at the no observed adverse effect level (NOAELs) (relative to the projected steady state AUC at the 115 mg dose in humans) were 11- and 2-fold, in rats and monkeys, respectively. Overall, the nonclinical program has sufficiently characterized the toxicity profile of GS-5718 and supports this study.

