1.2.3.1. Clinical Safety

As of November 20, 2020, GS-5718 has been administered to 62 healthy subjects in the FIH study.

GS-5718 in tablet form has been administered to healthy male and female subjects in single ascending doses (up to 150 mg; Part A: Cohorts 1-3 of GS-US-451-5399) and multiple ascending oral doses (up to 150 mg) for 10 days (Part C: Cohorts 6-8 of GS-US-451-5399). Part B of GS-US-451-5399 (Cohort 5) examined food effect and the potential for drug interactions with GS-5718 and a representative acid-reducing agent (omeprazole) with 50 mg single doses of GS-5718. Due to the ongoing nature of the study, it remains blinded to study subjects and the investigator but is unblinded to limited team members of the study sponsor.

GS-5718 has been well tolerated thus far during this study. No deaths, serious treatment-emergent adverse events (TEAEs), or TEAEs leading to study drug discontinuation were reported during the 6 months of the study. There have been no clinically relevant electrocardiogram (ECG) or vital sign abnormalities. When dosed with a single dose of GS-5718 at 150 mg, 1 subject experienced 2 TEAEs (headache and dyspepsia). Both events were Grade 1 in severity. When dosed with multiple doses of GS-5718 at 150 mg daily, 1 subject experienced 2 TEAEs (constipation and maculo-papular rash). The maculo-papular rash was related to the electrodes used for the ECG. Both events were Grade 1 in severity. All TEAEs were self-limited. There were no Grade 3 or 4 TEAEs in any cohorts of this study (Table 1-1).

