1.2.3.2. Pharmacokinetic Profile

Following single-dose administration of 15, 50, or 150 mg GS-5718 under fasting conditions, GS-5718 was absorbed rapidly with the maximum plasma concentration (C_{max}) occurring between 0.75 to 2 hours after dosing (median T_{max}). Following multiple-dose administration of 15, 50, or 150 mg once daily under fed conditions (standard breakfast), the median T_{max} ranged from 3 to 4 hours. Across the dose levels evaluated, GS-5718 exhibited a median $t_{1/2}$ of 25 to 33 hours following single and multiple doses. GS-5718 exposure (AUC and C_{max}) increased in an approximately dose proportional manner across the range of 15 mg to 150 mg. Consistent with the elimination half-life, GS-5718 exposure (AUC and C_{max}) accumulated following multiple, once-daily doses (1.6 to 2.4-fold for AUC and 1.5 to 2.5-fold for C_{max}). Steady-state appears to have been reached by Day 5 to 7.

Administration of GS-5718 with food (high-fat/high-calorie meal) resulted in delayed GS-5718 T_{max} (from 1 to 4 hours) with an approximately 18% reduction in mean C_{max} and no change in mean AUC. Omeprazole (with a 5-day pretreatment at 40 mg once daily dose) reduced mean C_{max} and AUC of GS-5718 by approximately 42% and 22%, respectively, with no change in the T_{max} of GS-5718.

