3.5.2. Study Drug Discontinuation Criteria

The sponsor medical monitor should be consulted prior to study drug discontinuation, when medically feasible.

Study drug should be permanently discontinued in the following circumstances:

- Any opportunistic infection
- Any Grade 2 or higher cardiovascular or hematologic event (or Grade 3 lymphopenia or anemia as described below under "Laboratory Criteria")
- Any serious infection that requires antimicrobial therapy or hospitalization, or any infection that meets SAE reporting criteria
- Unacceptable toxicity, or toxicity that, in the judgment of the investigator, compromises the subject's ability to continue study-specific procedures or is considered to not be in the subject's best interest
- Subject request to discontinue for any reason
- Subject noncompliance, per investigator judgment
- Investigator discretion
- Female subject becomes pregnant during the study
 - NOTE: If the female partner of a male subject becomes pregnant during the study, the investigator, in consultation with the Gilead medical monitor, will determine whether the subject should continue in the study on a case-by-case basis.
- Discontinuation of the study at the request of the study sponsor, a regulatory agency or an institutional review board (IRB)/independent ethics committee (IEC)

- Subject use of prohibited concurrent systemic therapy
- An absolute QTcF > 500 msec or a change from the baseline QTcF value > 60 msec
- Laboratory Criteria: After becoming aware of any of the abnormal laboratory values below, study drug should be paused, and an unscheduled visit (ie, sequential visit) should occur to retest within 3 to 7 days (except creatinine, which should be retested 7 to 14 days apart). Retest may be obtained sooner if medically indicated, per investigator judgment.
- If the laboratory abnormality is confirmed by the retest, then study drug should be permanently discontinued.
 - Hemoglobin < 8.0 g/dL (International System of Units [SI]: < 80.0 g/L)
 - ANC < 1500 cells/mm³ (SI: < 1.5 × 10⁹ cells/L)
 - Lymphocyte count < 500 cells/mm³ (SI: < 0.5 × 10⁹ cells/L)
 - Platelet count < 75,000 cells/mm³ (SI: < 75 × 10⁹ cells/L)
 - Any AST and/or ALT ≥ 3 × ULN independent of signs of liver damage
 - Estimated CL_{cr} < 60 mL/min based on the Cockcroft-Gault equation

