Appendix 3. Study Procedures Table

Procedure	Screening V0	Study Treatment Period				Early Termination ^b	Follow Up	Instructions
	-28*	Day 1	Week 1	Week 2	Week 4	Any	+28 Days ^a (±5 Days)	
Informed Consent	X							Written, signed, and dated informed consent must be obtained prior to screening
Inclusion/Exclusion Criteria	X	X						Documentation of select criteria must be submitted to the study sponsor for review and confirmation of subject eligibility
Medical History, Demographics, Substance Use	X							Medical history will include demographics, a review of surgical history, and CLE/SLE history
Prior and Concomitant Medications	X	X	X	X	X	X	X	
Height	X							Subjects should be instructed to remove shoes prior to baseline height measurement
Weight	X	X	X	X	X	X	X	
Vital Signs	X	X	X	X	X	X	X	Blood pressure, Pulse, Respiratory Rate, Temperature
12-Lead ECG	X			X	X	X	X	Resting ECG, performed and assessed locally; for subjects with chest lesions, study assessments should precede ECG, as applicable
Complete Physical Examination	X							
Symptom-Driven Physical Examination		X	X	X	X	X	X	Performed, as needed, based on signs and symptoms
CLASI Assessment	X	X	X	X	X	X	X	Subjects must have a CLASI activity (CLASI-A) score of ≥ 6 (excluding the alopecia component) during screening and Day 1

Procedure	Screening V0	Study Treatment Period				Early Termination ^b	Follow Up	Instructions
		Day 1	Week 1	Week 2	Week 4			
	-28 ^a	0 ^a	+7 Days ^a (±2 Days)	+14 Days ^a (±2 Days)	+28 Days ^a (±2 Days)	Any	+28 Days ^a (±5 Days)	
Photography of Skin Lesion(s)	X	X	X	X	X	X	X	Subject identifying features should be obscured, as much as possible. Follow-up photographs must target the same area of clinically active disease evaluated and photographed at baseline.
SLEDAI-2K Assessment		X		X	X	X	X	To be completed for subjects with concurrent SLE
Subject's Global Assessment	X	X	X	X	X	X	X	Subject's global assessment of CLE disease activity (visual analogue scale)
Physician's Global Assessment	X	X	X	X	X	X	X	Physician's global assessment of CLE disease activity (visual analogue scale)
Chemistry	X	X	X	X	X	X	X	See Appendix 6
Hematology	X	X	X	X	X	X	X	See Appendix 6
Fasting Lipids		X			X			No food or drinks, except water for at least 8 hours prior to blood sample collection
Serum Pregnancy Test	X							Females of childbearing potential only (see Appendix 4)
Urine Pregnancy Test		X	X	X	X	X	X	Females of childbearing potential only (see Appendix 4)

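### Do the Week 2 and Week 4 ECGs need a stated time relative to dosing?

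*Protocol*

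**What the plan says.** The 12-lead ECG row of Protocol Appendix 3 marks screening, Week 2, Week 4, early termination and follow-up. Its only instruction is "Resting ECG, performed and assessed locally; for subjects with chest lesions, study assessments should precede ECG, as applicable". SAP Appendix 1 repeats the row. One row of the schedule and its footnote c are redacted, but they are not the ECG row.

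Other rows do fix timing against the dose. Footnote d places the Week 4 PK samples predose and from 0.5 to 6 hours postdose, with windows in minutes. The Day 1 biopsies and many of the Day 1 biomarker samples are marked predose. Under Protocol 5.3 the Week 4 dose is taken on site, fasted. On other days, including Week 2, the dose is not tied to the visit.

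SAP 7.5 provides ECG listings by participant and visit, and SAP 7.5.1 gives the Fridericia formula. SAP 3 sorts listings by date and, where it applies, time. SAP 4.2.2 plans a listing of study drug administration.

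The one rule that acts on these ECGs is the discontinuation criterion in Protocol 3.5.2: "An absolute QTcF > 500 msec or a change from the baseline QTcF value > 60 msec".

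**The concern.** Safety is the primary objective, and the nonclinical section reports that "mild QT prolongation was observed at the high dose level in the cardiovascular safety pharmacology study in monkeys". The protocol rates the human risk as low "given the small magnitude of change and exposure margin at this dose level", and that margin (6-fold) is taken against projected free Cmax, a peak quantity. A reader would naturally want to know whether the on-treatment ECGs were recorded near peak.

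As written, a Week 4 ECG could be done before the on-site dose or at any point in the 6-hour PK stay. At Week 2 the interval since the home dose is open. A normal QTcF at trough reassures less than a normal QTcF at peak, and the specified listing does not separate them. The contrast with the minute-level PK timing in the same schedule makes the silence look like an oversight.

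**Working it through.** The plan gives no figure to reproduce. Two checks are possible: how far concentration could differ between an early and a late ECG, and what in the plan depends on the timing.

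**Inputs (Protocol 1.2.3.2).** Median half-life "of 25 to 33 hours following single and multiple doses". Median single-dose fasted Tmax "occurring between 0.75 to 2 hours after dosing". Median multiple-dose fed Tmax "ranged from 3 to 4 hours". Dosing is every 24 hours.

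**Trough relative to peak.** Assume one-compartment decline from Tmax to the next dose at steady state:

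trough/peak = 2^(−(24 − Tmax)/t½)

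| Tmax (h) | t½ = 25 h | t½ = 33 h |
|---|---|---|
| 0.75 | 2^(−23.25/25) = 0.525 | 2^(−23.25/33) = 0.614 |
| 2 | 2^(−22/25) = 0.543 | 2^(−22/33) = 0.630 |
| 3 | 2^(−21/25) = 0.559 | 2^(−21/33) = 0.643 |
| 4 | 2^(−20/25) = 0.574 | 2^(−20/33) = 0.657 |

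The range is about 53% to 66% overall, and 53% to 63% for the fasted Tmax values that match the Week 4 visit. A model with first-order absorption, tuned to Tmax of 1 to 4 h, gives 53% to 68%.

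**Within the Week 4 PK stay.** At 6 hours, the level relative to peak is 2^(−(6 − Tmax)/t½). With fasted Tmax of 0.75 to 2 h, this runs from 2^(−5.25/25) = 0.865 to 2^(−4/33) = 0.919. An ECG between Tmax and the last PK draw is therefore at about 86% of peak or more.

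**Model check.** Accumulation is 1/(1 − 2^(−24/t½)): 2.06 at 25 h and 2.53 at 33 h. The protocol states 1.6 to 2.4 for AUC and 1.5 to 2.5 for Cmax. The low end is not reproduced. An accumulation of 1.5 would need t½ = 24 × ln 2/ln 3 = 15.1 h, and trough would then be 2^(−23.25/15.1) to 2^(−20/15.1), about 34% to 40% of peak. So 53% to 66% shows scale and is not a limit.

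**Effect on the QT margin.** The 6-fold margin is already stated at peak. Measured against trough concentration it becomes 6/0.657 = 9.1 to 6/0.525 = 11.4. Timing decides whether an ECG is taken at a margin of about 6 or about 9 to 11.

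**Human data.** The healthy-volunteer study gave up to 150 mg daily for 10 days, which is 150/115 = 1.30 times this trial's dose, with approximately dose-proportional exposure. Protocol 1.2.3.1 reports: "There have been no clinically relevant electrocardiogram (ECG) or vital sign abnormalities". It does not say when those ECGs were taken relative to dose.

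**What depends on the timing.** The stated primary endpoints (Protocol 3.1 and 8.1.2) are counts of subjects with AEs and with laboratory abnormalities. The secondary endpoint is PK. No analysis in the visible text relates QTcF to concentration or to time after dose. The 3.5.2 criterion contains no timing term. SAP 8 drops PK analysis, and SAP 7.7 limits safety output because so few were enrolled. SAP 1 reports 3 participants, one of whom was terminated early, so there are at most 3 × 2 = 6 scheduled Week 2 and Week 4 tracings.

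**The case for a change.** The best case for acting is that the ECG listing is the only ECG output left in the SAP, each participant has only two on-treatment ECGs scheduled, and the subject is already on site at Week 4 with a timed dose. Placing the Week 4 ECG beside an early postdose PK draw would add no procedure, and a listing column would cost almost nothing. The omission is also genuine: redaction does not explain it, and SAP 3 refers at most to clock time.

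All of that stands as description, but the gain does not follow. A postdose Week 4 ECG gives up a tracing before that day's on-site dose and leaves Week 2 untimed. Its comparator would still be the screening ECG, the only one scheduled before treatment, up to 28 days earlier and with no set time of day. The natural slot of 1 to 2 hours rests on single-dose fasted Tmax, because the only multiple-dose Tmax given is fed. For this trial the visits can no longer be rearranged.

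That leaves the listing column. It depends on whether the eCRF captured ECG and dosing clock times, which the documents do not show. SAP 7.5 names no columns at all, so its silence on one is weak evidence that times will be absent. If the times exist, time since dose can be shown or worked out without amending the SAP. If they do not, no amendment can recover them.

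**Conclusion.** The omission is real, and no change to the plan is warranted. Without dose-relative timing, a listed Week 2 or Week 4 QTcF cannot be placed between trough and peak from the specified output alone. The likely swing is moderate: trough at about 53% to 66% of peak, assuming one-compartment decline with the protocol's median half-life and Tmax, and lower if the low-end accumulation figures are the better guide. Either way, no stated endpoint, rule or number comes out wrong when the plan is followed, because these are resting, locally read safety ECGs and the QTcF criterion holds at any time of day.

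In the abbreviated report the effect is confined to how a handful of tracings from 3 participants are annotated, with no PK results beside them. This rests on the visible text: the exploratory objectives are redacted, and the eCRF was not available.

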Appendix 5. Management of Laboratory Adverse Events

Refer to the clinical and laboratory study drug discontinuation criteria outlined in Section 3.5.

* Not applicable for Neutrophil, Platelet, AST, ALT, or Creatinine Clearance

** Not applicable for Neutrophil, Platelet, AST, ALT, Creatinine Clearance, Hemoglobin decrease or Lymphocyte decrease

Appendix 6. Clinical Laboratory Assessment Table

[figure not shown]
Hematology	Chemistry	Urinalysis	Lipid Profile	Other Tests
Differentials (absolute and percentage), including but not limited to: Lymphocytes Monocytes Neutrophils Eosinophils Basophils Hematocrit Hemoglobin Platelet count Red blood cell count Red blood cell indices Reticulocyte count White blood cell count	Alanine aminotransferase Alkaline phosphatase Aspartate aminotransferase Bilirubin, direct and indirect Bilirubin, total Gamma-glutamyl transpeptidase Total protein Albumin Blood urea nitrogen Bicarbonate Calcium Chloride Creatine Kinase Creatinine Creatinine clearance Cystatin C Glucose Magnesium Phosphorus Potassium Sodium Uric acid (at screening only)	Appearance Blood Bilirubin Color Glucose Ketones Leukocyte esterase Nitrite pH Protein Specific gravity Urine protein to creatinine ratio Urobilinogen	High-density lipoprotein Low-density lipoprotein Total cholesterol Triglycerides	Autoantibody tests: Anti-nuclear antibody Anti-double-stranded DNA Antiphospholipid antibodies Anti-RNP Anti-Sm Anti-SSA/Ro Anti-SSB/La Complement levels (C3, C4, and CH50) Follicle-stimulating hormone (as applicable) Plasma PK QuantiFERON®-TB Gold In-Tube test* Quantitative immunoglobulins (IgG, IgM, and IgA) Urine drug screen for: Alcohol Amphetamines Barbiturates Benzodiazepines Opiates CCI
		Pregnancy In females of childbearing potential: Serum pregnancy test Urine pregnancy test	Virology Hepatitis B surface antigen Hepatitis B virus core antibody Hepatitis C Virus antibody (if positive, then reflex HCV RNA) Human immunodeficiency virus antibody	

* Not required for subjects with prior latent TB who have been treated with a full course of prophylaxis.

All labs will be assayed and calculated by a sponsor-designated laboratory unless otherwise specified, in accordance with the time points detailed in the Study Procedures Table (Appendix 3)

Unscheduled laboratory tests may be performed at the discretion of the investigator; if the test(s) is performed to evaluate laboratory results to resume study drug, samples must also be submitted to the sponsor-designated laboratory.

Appendix 7. EULAR/ACR 2019 Classification Criteria for Systemic Lupus Erythematosus

Appendix 8. Cutaneous LE Disease Area and Severity Index (CLASI)

Cutaneous LE Disease Area and Severity Index (CLASI) ©

Select the score in each anatomical location that describes the most severely affected cutaneous lupus-associated lesion

← activity
← damage →

[figure not shown]
Anatomical Location	Erythema	Scale/ Hypertrophy	Dyspigmentation	Scarring/ Atrophy/ Panniculitis	Anatomical Location
	0-absent 1-pink; faint erythema 2- red; 3-dark red; purple/violaceous/ crusted/ hemorrhagic	0-absent; 1-scale 2-verrucous/ hypertrophic	0-absent, 1-dyspigmentation	0 - absent 1 - scarring 2 - severely atrophic scarring or panniculitis	
Scalp				See below	Scalp
Ears					Ears
Nose (incl. malar area)					Nose (incl. malar area)
Rest of the face					Rest of the face
V-area neck (frontal)					V-area neck (frontal)
Post. Neck &/or shoulders					Post. Neck &/or shoulders
Chest					Chest
Abdomen					Abdomen
Back, buttocks					Back, buttocks
Arms					Arms
Hands					Hands
Legs					Legs
Feet					Feet

Mucous membrane	Dyspigmentation
Mucous membrane lesions (examine if patient confirms involvement)	Report duration of dyspigmentation after active lesions have resolved (verbal report by patient – tick appropriate box)
0-absent; 1-lesion or ulceration	 Dyspigmentation usually lasts less than 12 months (dyspigmentation score above remains)  Dyspigmentation usually lasts at least 12 months (dyspigmentation score is doubled)

Alopecia

Recent Hair loss
(within the last 30 days / as reported by patient)

1-Yes
0-No

NB: if scarring and non-scarring aspects seem to coexist in one lesion, please score both

Divide the scalp into four quadrants as shown. The dividing line between right and left is the midline. The dividing line between frontal and occipital is the line connecting the highest points of the ear lobe. A quadrant is considered affected if there is a lesion within the quadrant.

Alopecia (clinically not obviously scarred)	Scarring of the scalp (judged clinically)
0-absent 1-diffuse; non-inflammatory 2-focal or patchy in one quadrant; 3-focal or patchy in more than one quadrant	0- absent 3- in one quadrant 4- two quadrants 5- three quadrants 6- affects the whole skull


Total Activity Score (For the activity score please add up the scores of the left side i.e. for Erythema, Scale/Hypertrophy, Mucous membrane involvement and Alopecia)
 

	
Total Damage Score (For the damage score, please add up the scores of the right side, i.e. for Dyspigmentation, Scarring/Atrophy/Panniculitis and Scarring of the Scalp)
 

--	--

Appendix 9. Systemic Lupus Erythematosus Disease Activity Index 2000 (SLEDAI-2K)

Study No.: _____ Patient Name: _____ Visit Date: _____

(Enter weight in SLEDAI Score column if descriptor is present at the time of the visit or in the preceding 10 days.)

Weight	SLEDAI SCORE	Descriptor	Definition
8	_____	Seizure	Recent onset, exclude metabolic, infectious or drug causes.
8	_____	Psychosis	Altered ability to function in normal activity due to severe disturbance in the perception of reality. Include hallucinations, incoherence, marked loose associations, impoverished thought content, marked illogical thinking, bizarre, disorganized, or catatonic behavior. Exclude uremia and drug causes.
8	_____	Organic brain syndrome	Altered mental function with impaired orientation, memory, or other intellectual function, with rapid onset and fluctuating clinical features, inability to sustain attention to environment, plus at least 2 of the following: perceptual disturbance, incoherent speech, insomnia or daytime drowsiness, or increased or decreased psychomotor activity. Exclude metabolic, infectious, or drug causes.
8	_____	Visual disturbance	Retinal changes of SLE. Include cytoid bodies, retinal hemorrhages, serous exudate or hemorrhages in the choroid, or optic neuritis. Exclude hypertension, infection, or drug causes.
8	_____	Cranial nerve disorder	New onset of sensory or motor neuropathy involving cranial nerves.
8	_____	Lupus headache	Severe, persistent headache; may be migrainous, but must be nonresponsive to narcotic analgesia.
8	_____	CVA	New onset of cerebrovascular accident(s). Exclude arteriosclerosis.
8	_____	Vasculitis	Ulceration, gangrene, tender finger nodules, periungual infarction, splinter hemorrhages, or biopsy or angiogram proof of vasculitis.
4	_____	Arthritis	≥ 2 joints with pain and signs of inflammation (i.e., tenderness, swelling or effusion).
4	_____	Myositis	Proximal muscle aching/weakness, associated with elevated creatine phosphokinase/aldolase or electromyogram changes or a biopsy showing myositis.
4	_____	Urinary casts	Heme-granular or red blood cell casts.
4	_____	Hematuria	>5 red blood cells/high power field. Exclude stone, infection, or other cause.
4	_____	Proteinuria	>0.5 gram/24 hours
4	_____	Pyuria	>5 white blood cells/high power field. Exclude infection.
2	_____	Rash	Inflammatory type rash.
2	_____	Alopecia	Abnormal, patchy or diffuse loss of hair.
2	_____	Mucosal ulcers	Oral or nasal ulcerations.
2	_____	Pleurisy	Pleuritic chest pain with pleural rub or effusion, or pleural thickening.
2	_____	Pericarditis	Pericardial pain with at least 1 of the following: rub, effusion, or electrocardiogram or echocardiogram confirmation.
2	_____	Low complement	Decrease in CH50, C3, or C4 below the lower limit of normal for testing laboratory
2	_____	Increased DNA binding	Increased DNA binding by Farr assay above normal range for testing laboratory.
1	_____	Fever	>38° C. Exclude infectious cause.
1	_____	Thrombocytopenia	<100,000 platelets / x10 ⁹ /L, exclude drug causes.
1	_____	Leukopenia	< 3,000 white blood cells / x10 ⁹ /L, exclude drug causes.
TOTAL SLEDAI SCORE _____			

